4.6.2 Other Prohibited and/or Restricted Treatments

Prohibited and/or restricted medications taken prior to study drug administration and during the study are described below, and washout requirements are provided in [APPENDIX 4](#). Medications taken within 30 days prior to screening must be recorded on the eCRF.

1. Prior exposure to BOS161721
2. Patients who have received treatment with anti-CD20 monoclonal antibodies within 24 weeks of screening; recovery of B cells (CD19+) must be documented (record absolute number of CD19+ B cells)
3. Patients who have received treatment with cyclophosphamide within the 24 weeks prior to screening
4. Patients who have received treatment with cyclosporine (with exception of ophthalmic use), any other calcineurin inhibitor or other immunosuppressive medication not specified in the inclusion criteria within 4 weeks for oral use or 8 weeks for topical use of screening
5. Patients who are currently receiving or are scheduled to receive plasmapheresis or lymphapheresis therapy, or have received such therapy within 24 weeks prior to screening
6. Patients who have received any live vaccines within 30 days of screening. Note: Furthermore, live vaccines should not be used during the course of the study and within the 2 months following last dose. Other inactivated vaccines such as tetanus, etc., may be used according to local guidelines during treatment period
7. Patients who are scheduled or anticipated to have elective surgery during the course of the study
8. Initiation of new immunosuppressant or anti-malarial agent is not permitted. Note: Dose reduction or replacement may be allowed due to intolerability or shortage for patients on a stable dose prior to study initiation

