Blood samples were collected at every in-house study visit for BOS161721 concentration determinations. Blood samples were also collected for determination of IL-21 plasma levels (free and total). Safety was assessed based on the occurrence of treatment-emergent AEs, hepatic function abnormality, and acute and delayed hypersensitivity reactions. Other safety variables included ECGs, vital signs (blood pressure [BP], heart rate, and temperature), safety laboratory assessments, blood sampling for ADAs, total IgG and immunoglobulin M (IgM) levels, CD4+ count, and full and targeted physical examinations. Overall, there were no clinically significant findings from this study. Adverse events reported as related to the study drug, particularly infections, were expected for the compound, and there were no clinically relevant changes in laboratory and ECG results or vital signs. There was 1 serious adverse event (SAE; death due to pulmonary embolism) that occurred 127 days after a single administration of 240 mg SC dose of BOS161721. The causality of this single SAE was not attributed to study drug and further information can be found in the Investigator's Brochure. Final PK data from the SAD study demonstrates BOS161721 has a mean $t_{1/2}$ ranging from 80 to 87 days for doses of ≥ 30 mg in healthy subjects.

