1.2.3 Study Dose Selection

Doses have been selected for the multiple ascending dose (MAD) Phase 1b portion based on a 90-day safety, tolerability, PK, and PD data review from the Phase 1 SAD study (BOS161721-01); the SDMT reviewed the blinded safety data from subjects for each dose cohort (8 cohorts, evaluating 1 [IV], 3 [SC], 10 [SC], 22 [IV], 30 [SC], 60 [SC], 120 [SC], or 240 [SC] mg), along with the accumulated safety and available PK/PD data from all subjects in the previous dose cohorts, to make a decision on whether to proceed to the next higher dose level, repeat a dose level, or stop dose escalation. Overall, there were no clinically significant safety or tolerability findings from this study.

Based on the Day-90 interim cut of the PK and biomarker data in the BOS161721-01 study, the recommended doses for evaluation in the MAD portion of this study are 20, 60, and 120 mg SC monthly. This dose recommendation is supported by evidence of linear PK with BOS161721 resulting in a median first time to maximum concentration (T_{max}) of 6 days and an apparent terminal half-life of 44 days. Furthermore, pSTAT3 suppression, a marker of IL-21 target engagement, follows a similar time course of the mAb levels, with maximal and sustained suppression apparent with doses greater than 30 mg SC (Figure 1).

Figure 1. Individual pSTAT3 C_{min} Levels Versus Dose

IV = intravenous, pSTAT3 = phosphorylated signal transducer and activator of transcription 3; SC = subcutaneous

All doses selected for the MAD portion are projected not to exceed the mean exposure of that achieved following the highest single dose of 240 mg SC administered in the Phase 1 SAD study. Cohort 1 will include randomized treatment to the 20 mg dose. Based on the staggered study design, the data monitoring committee (DMC) will perform a scheduled review of safety data and sequentially consider dose escalation for Cohorts 2 and 3. In addition, the DMC and Boston Pharmaceuticals will conduct a data review to determine which dose will be carried forward into the proof of concept (POC) Phase 2 portion. This POC dose decision will be based on evaluation of the PK, safety (inclusive of dose-limiting toxicity [DLT]), and tolerability data (and available PD/biomarker data) from Cohorts 1, 2 and 3 from the MAD portion (see [Section 3.1.2.1](#) for the chosen POC dose and justification).

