3 STUDY PLAN

3.1 Study Design

This is a Phase 1b/2 combined, randomized, multicenter, double-blind, placebo-controlled trial to study the clinical efficacy, safety, and PK of SC doses of BOS161721 in adult patients with moderately to severely active SLE. After successfully completing a screening phase, eligible patients will be randomized to a specified dose of BOS161721 or placebo. The dosing schedule will be monthly.

The trial will consist of 2 double-blinded portions: MAD Phase 1b and POC Phase 2. Patients may receive a total of 7 SC monthly doses of study drug on Days 0, 30, 60, 90, 120, 150, and 180, followed by safety follow-up visits at Days 210, 240, and 270.

SLE disease activity assessment data will be centrally reviewed by medical monitor and sponsor to ensure the scores are clinically meaningful and compliant with specific definition. The scope of responsibility includes, but is not limited to, review and confirmation of “A” and “B” BILAG system organ disease, confirmation of clinical components of the SLEDAI-2K score at screening and during the study, and cross-validation of the instruments used in this study to assess the disease activity. Further details on the content and methods of data reports by the medical monitor and sponsor will be outlined in the Medical Data Review Plan along with the processes and procedures that will be followed.

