4.7.2 Contraception

WOCBP must agree to follow instructions for method(s) of contraception for the duration of treatment with study drug plus 52 weeks, due to the mean terminal $\frac{1}{2}$ life of the study drug.

Men who are sexually active with WOCBP must agree to follow instructions for method(s) of contraception for the duration of treatment with study drug plus 52 weeks, due to the mean terminal $\frac{1}{2}$ life of the study drug.

Investigators shall counsel WOCBP and men who are sexually active with WOCBP on the importance of pregnancy prevention and the implications of an unexpected pregnancy. Investigators shall advise WOCBP and men who are sexually active with WOCBP on the use of highly effective methods of contraception. Highly effective methods of contraception have a failure rate of < 1% when used consistently and correctly.

At a minimum, patients must agree to the use of 1 method of highly effective contraception from the following:

- Male condoms with spermicide
- Hormonal methods of contraception including combined oral contraceptive pills, vaginal ring, injectables, implants, and intrauterine devices (IUDs) such as Mirena[®] by patients who are WOCBP or a male patient's WOCBP partner. Women who are partner of men who are patients participating in the study may use hormone-based contraceptives as 1 of the acceptable methods of contraception since they will not be receiving study drug.
- IUDs, such as ParaGard[®]
- Vasectomy
- Complete abstinence, defined as complete avoidance of heterosexual intercourse, is an acceptable form of contraception. Women who are abstinent while participating in the study must continue to have pregnancy tests. Acceptable alternate methods of highly effective contraception must be discussed in the event that the patient chooses to forego complete abstinence.

Azoospermic men and WOCBP who are continuously not heterosexually active are exempt from contraceptive requirements. However, WOCBP must still undergo pregnancy testing.

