6.2.2.7.1 Reporting of Pregnancy

As information is available, a pregnancy diagnosed during the study will be reported within 24 hours to the sponsor via the Pregnancy Notification and Outcome Form, including pregnancy in female patients who received study drug and female partners of male study patients who received study drug. The pregnancy should be followed to term and/or outcome and this outcome should also be reported to the sponsor via the Pregnancy Notification and Outcome Form. Pregnancy itself is not regarded as an AE or SAE unless there is complication.

In the case of a live birth, the structural integrity of the neonate can be assessed at the time of birth. In the event of a termination, the reason(s) for termination should be specified and, if clinically possible, the structural integrity of the terminated fetus should be assessed by gross visual inspection (unless pre-procedure test findings are conclusive for a congenital anomaly and the findings are reported).

If the outcome of the pregnancy meets the criteria for an AE or SAE (ie, ectopic pregnancy, spontaneous abortion, intrauterine fetal demise, neonatal death, or congenital anomaly [in a live born, a terminated fetus, an intrauterine fetal demise, or a neonatal death]), the investigator should follow the procedures for reporting SAEs.

Additional information about pregnancy outcomes that are reported as SAEs follows:

- Spontaneous abortion includes miscarriage and missed abortion
- Neonatal deaths that occur within 1 month of birth should be reported, without regard to causality, as SAEs. In addition, infant deaths after 1 month should be reported as serious

adverse events when the investigator assesses the neonatal death as related or possibly related to exposure to investigational product.

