6.2.2.7.2 Reporting of Serious Adverse Events

The principal investigator is responsible for providing notification to the sponsor of any SAE via the Safety Adverse Event Form, whether deemed study drug related or not, that a patient experiences during their participation in this study within 24 hours of becoming aware of the event.

If an SAE is fatal or life threatening, notification to the sponsor must be made aware immediately, irrespective of the extent of available AE information. This timeframe also applies to additional new information (follow-up) on previously forwarded SAE reports as well as to the initial and follow-up reporting of exposure during pregnancy and exposure via breastfeeding cases. In the rare event that the investigator does not become aware of the occurrence of an SAE immediately (eg, if an outpatient study patient initially seeks treatment elsewhere), the investigator is to report the event within 24 hours after learning of it and document the time of his/her first awareness of the AE.

The principal investigator will review each SAE and evaluate the intensity and the causal relationship of the event to the study drug. All SAEs will be recorded from the time of first dose of study drug through the safety follow-up period (up to Day 270). SAEs occurring after the final follow-up visit and coming to the attention of the principal investigator must be reported only if there is (in the opinion of the principal investigator) reasonable causal relationship with the study drug.

As a minimum requirement, the initial notification should provide the following information:

- Study number
- Patient number
- Details of the SAE (verbatim details are sufficient for immediate notification)
- Criterion for classification as ‘serious’
- Causality assessment (which may be updated in a follow-up report when sufficient information is available to make this classification)

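### Contraception is required to about Day 544 because of the half-life, but there is no clear duty to report a pregnancy after Day 270

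*Protocol*

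**What the plan says.** The current protocol (Version 5.0) contains these statements.

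- **Half-life.** Section 1.2.2.3 reports a final mean terminal half-life "ranging from 80 to 87 days for doses of ≥ 30 mg in healthy subjects". Section 1.2.3 still carries "an apparent terminal half-life of 44 days", from the Day-90 interim cut.
- **Dosing.** Section 3.1 allows up to seven "monthly doses of study drug on Days 0, 30, 60, 90, 120, 150, and 180", so the last dose falls on Day 180.
- **Contraception.** Section 4.7.2 requires it, for women of childbearing potential and for men with such partners, "for the duration of treatment with study drug plus 52 weeks, due to the mean terminal" half-life of the drug. No figure for the half-life is given there.
- **Pregnancy testing.** Section 6.2.1.1 places the last scheduled urine test at the last follow-up visit, Day 270.
- **Pregnancy reporting.** Section 6.2.2.7.1 says "a pregnancy diagnosed during the study will be reported within 24 hours to the sponsor". Section 3.5 defines two ends of study: the individual patient's, at the last visit or at withdrawal, and the trial's, at the last visit of the last patient.
- **SAEs.** Under Section 6.2.2.7.2, "All SAEs will be recorded from the time of first dose of study drug through the safety follow-up period (up to Day 270". Later SAEs are reported only if the investigator sees a reasonable causal link, with no end date.
- **Live vaccines.** Section 4.6.2, item 6: "live vaccines should not be used during the course of the study and within the 2 months following last dose".

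**The concern.** The contraception rule treats exposure as a matter for concern for a year after treatment. The pregnancy-reporting rule is tied to the study, which for an individual patient ends 90 days after the last dose. A pregnancy in the months between falls in a period when the protocol itself asks patients to avoid conception, yet nothing clearly obliges the site to report it. Section 1.2.5.9 says no preclinical reproductive toxicity data are available, so these are the exposures about which least is known, and an unreported exposed pregnancy cannot be reliably recovered later.

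Two other limits after the last dose raise the same question on a smaller scale. The live-vaccine sentence gives two end points that do not coincide. SAE reporting after Day 270 passes through a causality judgement, and Section 6.2.2.4 defines a related event as one that concurrent disease or other drugs cannot explain, a demanding test in SLE patients on background therapy. The only SAE in the single-dose study came 127 days after dosing and was not attributed to drug (Section 1.2.2.3). The same interval after a Day 180 dose would be Day 307, beyond all-cause recording.

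**Working it through.** **Inputs.** Last dose Day 180 (3.1); last visit 90 days later (6.2.1.1); contraception for 52 weeks after treatment (4.7.2), counted here from the last dose; half-life T = 80 to 87 days (1.2.2.3), with 44 days (1.2.3) for comparison.

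**The plan's own figure.** 180 + 90 = 270, so the stated Day 270 reproduces.

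**End of contraception.** 52 × 7 = 364 days; 180 + 364 = Day 544.

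**Length of the gap.** 544 − 270 = 274 days; 274 / 7 = 39.1 weeks.

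**Drug remaining.** With first-order decline, the fraction left t days after the last dose is 2^(−t/T).

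| Time after last dose | T = 80 | T = 87 | T = 44 |
|---|---|---|---|
| 60 days | 0.595 (0.75 half-lives) | 0.620 (0.69) | 0.389 (1.36) |
| 90 days (Day 270) | 0.459 (1.12) | 0.488 (1.03) | 0.242 (2.05) |
| 364 days (Day 544) | 0.043 (4.55) | 0.055 (4.18) | 0.003 (8.27) |

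At Day 270, therefore, 46-49% remains after 1.0-1.1 half-lives. At the end of contraception 4-6% remains. The 52 weeks is itself a little short of five half-lives (5 × 80 = 400 days to 5 × 87 = 435 days, or 57.1 to 62.1 weeks), and the protocol gives no formula for it.

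**What the study can mean in Section 6.2.2.7.1.** If it is the patient's own study, the gap is 274 days for every completer. If it is the whole trial, the gap is 274 days minus the time from that patient's Day 270 to the last patient's last visit, and never below zero. A patient who finishes last has the full 274 days, and one who finishes at least 274 days before the last visit of the trial has none. The duty then depends on enrolment date.

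**Live vaccines.** For a completer the course of the study runs to Day 270, past the 2-month point at about Day 240 (180 + 60). For a patient who withdraws early, Section 3.5 treats the study as ended while Section 5.5 still schedules a visit 90 days after dosing. The 2-month limit can then be the operative one, with 59-62% of the last level remaining.

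**Provenance only.** The Version 4.0 amendment log gives a 41-day half-life as the reason for adding the Day 270 pregnancy test; 90 / 41 = 2.2 half-lives, with 22% remaining. The Version 4.0 contraception periods of 36 and 44 weeks match (5 × 44 + 30) / 7 = 35.7 and (5 × 44 + 90) / 7 = 44.3 weeks. Contraception was revised together with the half-life, while the pregnancy test and reporting windows kept their timing. The change between versions is not itself an error.

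**The case against.** The best defence is that no stated standard is breached. The protocol nowhere says that vaccine, SAE or follow-up windows must span a given number of half-lives; the five-half-life heading in Appendix 4 concerns washout of other drugs before consent. Contraception addresses fetal exposure, and different risks may properly have different windows. This stands, and it makes the point one of unreconciled provisions.

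Three stronger readings are tempting, and the text does not support them.

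- A reader might infer that SAE capture closes at Day 270. Only all-cause recording does. Related SAEs stay reportable with no end date, including a congenital anomaly judged related, and Section 6.2.2.8 follows every SAE to resolution or stability, or until the patient is lost to follow-up.
- A reader might infer that live vaccines are barred for only 2 months. The sentence also bars them throughout the study, so the 60-day residual figures do not describe a completer.
- A reader might infer that IL-21 signalling is still maximally suppressed at Day 270. Under linear kinetics the seven doses accumulate by (1 − 2^(−210/T)) / (1 − 2^(−30/T)) = 3.66 to 3.82 times 120 mg, leaving 201-224 mg at Day 270, and Section 1.2.3 describes "maximal and sustained suppression apparent with doses greater than 30 mg SC". But that describes single administered doses in healthy subjects at an interim cut. The protocol states no residual-amount or concentration threshold and does not carry the observation over to accumulated drug in SLE patients.

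It can also be said that the study in the pregnancy rule may mean the whole trial. That narrows the gap for early enrolees but leaves it at full length for the last ones, so the wording still needs attention.

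**Conclusion.** The point holds for pregnancy reporting. The protocol requires contraception to about Day 544 on the ground of the half-life, but scheduled testing ends at Day 270 and there is no clear reporting duty for the following 274 days, about 39 weeks, on the individual reading of end of study. On the whole-trial reading the uncovered period runs from none to 39 weeks according to enrolment date. At Day 270 about 46-49% of the drug remains.

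The residual figures assume first-order decline and the half-life from single doses in healthy subjects; the documents do not give the half-life in SLE patients. The length of the gap needs neither assumption, only that treatment ends with the Day 180 dose.

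The live-vaccine sentence and the related-only rule for late SAEs are secondary. The first holds two limits that must be reconciled; the second is a permissible design choice whose basis is not stated. The whole is a moderate matter of internal consistency in safety reporting and does not affect the efficacy analysis.

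**What to change.** Reword Section 6.2.2.7.1 so that the duty to report and follow a pregnancy, in a patient or a male patient's partner, covers the contraception period the protocol already sets in Section 4.7.2. The existing Pregnancy Notification and Outcome Form serves and no visit is added. The cost is a passive reporting duty for sites for about 39 more weeks, and a consent or site-letter update.

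Separately, the sponsor should state one half-life basis and reconcile with it Sections 1.2.2.3, 1.2.3, 4.6.2 item 6, 4.7.2, 6.2.1.1, 6.2.2.7.1 and 6.2.2.7.2, including which of the two live-vaccine limits applies after early discontinuation. The vaccine interval and the SAE window are for the sponsor's clinical team to decide; none is proposed here.

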4.7 Women of Childbearing Potential

WOCBP is defined as any woman who has experienced menarche and who has not undergone surgical sterilization (hysterectomy, bilateral tubal ligation, or bilateral oophorectomy) and is not postmenopausal.

See [Section 4.7.2](#) for detailed information regarding contraceptive requirements for WOCBP.

4.7.1 Determination of Menopause

Menopause is defined as at least 12 months of amenorrhea in a woman over age 45 in the absence of other biological or physiological causes. Women under the age of 55 years must have a documented serum FSH level > 40 mIU/mL at screening to confirm menopause.

4.7.2 Contraception

WOCBP must agree to follow instructions for method(s) of contraception for the duration of treatment with study drug plus 52 weeks, due to the mean terminal $\frac{1}{2}$ life of the study drug.

Men who are sexually active with WOCBP must agree to follow instructions for method(s) of contraception for the duration of treatment with study drug plus 52 weeks, due to the mean terminal $\frac{1}{2}$ life of the study drug.

Investigators shall counsel WOCBP and men who are sexually active with WOCBP on the importance of pregnancy prevention and the implications of an unexpected pregnancy. Investigators shall advise WOCBP and men who are sexually active with WOCBP on the use of highly effective methods of contraception. Highly effective methods of contraception have a failure rate of < 1% when used consistently and correctly.

At a minimum, patients must agree to the use of 1 method of highly effective contraception from the following:

- Male condoms with spermicide
- Hormonal methods of contraception including combined oral contraceptive pills, vaginal ring, injectables, implants, and intrauterine devices (IUDs) such as Mirena[®] by patients who are WOCBP or a male patient's WOCBP partner. Women who are partner of men who are patients participating in the study may use hormone-based contraceptives as 1 of the acceptable methods of contraception since they will not be receiving study drug.
- IUDs, such as ParaGard[®]
- Vasectomy
- Complete abstinence, defined as complete avoidance of heterosexual intercourse, is an acceptable form of contraception. Women who are abstinent while participating in the study must continue to have pregnancy tests. Acceptable alternate methods of highly effective contraception must be discussed in the event that the patient chooses to forego complete abstinence.

Azoospermic men and WOCBP who are continuously not heterosexually active are exempt from contraceptive requirements. However, WOCBP must still undergo pregnancy testing.

